9.0 Vulnerable Populations

9.1 Vulnerable Populations:

Population / Group	Identify whether any of the following populations will be targeted, included (not necessarily targeted) or excluded from participation in the study.
Children	Excluded from Participation
Pregnant women/fetuses/neonates	Excluded from Participation
Prisoners	Excluded from Participation
Adults lacking capacity to consent and/or adults with diminished capacity to consent, including, but not limited to, those with acute medical conditions, psychiatric disorders, neurologic disorders, developmental disorders, and behavioral disorders	Excluded from Participation
Non-English speakers	Excluded from Participation
Those unable to read (illiterate)	Excluded from Participation
Employees of the researcher	Excluded from Participation
Students of the researcher	Excluded from Participation
Undervalued or disenfranchised social group	Excluded from Participation

MEDICAL PROTOCOL (HRP-590)

PROTOCOL TITLE: Exercise and the Gut Microbiome R21

VERSION DATE: 05/11/2022

Active members of the military (service members), DoD personnel (including civilian employees)	Excluded from Participation
Individual or group that is approached for participation in research during a stressful situation such as emergency room setting, childbirth (labor), etc.	Excluded from Participation
Individual or group that is disadvantaged in the distribution of social goods and services such as income, housing, or healthcare.	Excluded from Participation
Individual or group with a serious health condition for which there are no satisfactory standard treatments.	Excluded from Participation
Individual or group with a fear of negative consequences for not participating in the research (e.g. institutionalization, deportation, disclosure of stigmatizing behavior).	Excluded from Participation
Any other circumstance/dynamic that could increase vulnerability to coercion or exploitation that might influence consent to research or decision to continue in research.	Excluded from Participation

9.2 Additional Safeguards: N/A**10.0 Local Number of Participants**

10.1 Local Number of Participants to be Consented: We will recruit participants on a rolling basis with the help of our clinical partners within community-based health clinics and community outreach around Minneapolis-St. Paul. We will assume a 20% attrition rate based on documented attrition rates of PA interventions,⁸²⁻⁸⁴ along with a 30% rate of individuals who fail to fall within the HbA1c eligibility range during screening. With these rates in mind, we will recruit 150 individuals total to meet our desired overall N of 100 participants (n = 50 per group). Given the need for participants to be

MEDICAL PROTOCOL (HRP-590)

PROTOCOL TITLE: Exercise and the Gut Microbiome R21

VERSION DATE: 05/11/2022

able to participant in the exercise intervention at the Epidemiology Clinical Research Center, all participants will be recruited locally.

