1.0 Objectives

1.1 **Purpose:** We propose a 100-participant randomized controlled 2-arm parallel trial which employs a metagenomic approach to examine how 8 weeks of supervised moderate-intensity treadmill walking exercise (MWE)^{1,2} for 30-45 min 3 times/week alters the gut microbiome, serum SCFAs, and the cardiometabolic profile, body weight, and body composition of individuals 30-64 years old who are overweight or obese and have PreD.

Aim 1: Compare the effect of 8 weeks of MWE vs. control on shifts in the gut microbiome of overweight or obese individuals with PreD. **H1:** Gut microbial diversity and functional capacity (specifically, genes relevant to SCFA production) will increase improve after 8 weeks in the experimental group vs. control.

Aim 2: Compare the effect of 8 weeks of MWE vs. control on changes in serum SCFAs. **H2:** Serum Levels of SCFAs butyrate, acetate, and propionate will increase after 8 weeks in the experimental group vs. control.

Aim 3: Use formal mediation methods to estimate the proportion of MWE-induced changes in participants' cardiometabolic profiles, body weight, and body composition that are mediated by changes in the gut microbiome and/or serum SCFAs. **H3:** MWE-induced changes in the gut microbiome and serum SCFAs will partly explain changes in participants' cardiometabolic profile (e.g., blood lipids, fasting insulin/glucose, blood pressure, waist circumference), body weight, and body composition.

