4.0 Study Intervention(s)/Investigational Agent(s)

4.1 **Description:** Following baseline data collection, participants will be randomized into one of two study groups using PROC PLAN (SAS 9.4) and a 1:1 allocation ratio.

GROUP 1 (aka, Experimental group): participants will complete 3 walking sessions/week for a total of 8 weeks (24 total sessions). Walking sessions will either take place on new commercial treadmills in the Epidemiology Clinical Research Center or remotely at or around a participant's home (see below). Regardless of the walking location, walking sessions will be 30 min in duration during intervention weeks 1 through 4 and a minimum of 45 min each during intervention weeks 5 through 8.

GROUP 2 (aka, Control group): participants will be asked to maintain their usual PA during the initial 8-week intervention period but will undergo all data collection procedures as outlined for the experimental group (See Section 5.2).

Experimental group participants who want to forego in-person exercise sessions on the University of Minnesota campus due to logistical constraints or the COVID-19 pandemic will modify the exercise intervention in the following manner:

MEDICAL PROTOCOL (HRP-590)

PROTOCOL TITLE: Exercise and the Gut Microbiome R21

VERSION DATE: 05/11/2022

Experimental group participants will engage in the same frequency and duration of walks as described above, but with a change in location to either: (a) in neighborhood or backyard walk (weather permitting, maintaining physical distancing); (b) on a treadmill within their home; and (c) in the hallway of their home if options a. and b. are not possible.

To monitor physical activity levels and ensure remote compliance: we will monitor to ensure that participants are completing their home-based walks at the proper duration and intensity using the Fitabase® platform. (See more information on the data security of Fitabase® in Section 16.7)

4.2 **Drug/Device Handling:** N/A

4.3 **Biosafety:** N/A

4.4 **Stem Cells:** N/A

5.0 **Procedures Involved**

5.1 **Study Design:** We will employ a 100-participant, 8-wk, randomized 2-arm parallel trial design with a 1:1 allocation ratio.

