15.0 Statistical Considerations

15.1 Data Analysis Plan: Chi-square and independent *t*-tests will evaluate baseline group differences as appropriate. Mediation analyses will also be conducted. We outline our analysis plans in Section 15.3. ⁸⁶⁻⁹²

MEDICAL PROTOCOL (HRP-590)

PROTOCOL TITLE: Exercise and the Gut Microbiome R21

VERSION DATE: 05/11/2022

15.2 Power Analysis: Power for Aim 1 is based on analyses using alpha-diversity (Shannon Index) as the primary outcome. Taniguchi et al.⁴⁶, reported a mean \pm SD baseline Shannon Index of 5.7 ± 0.6 which is consistent with preliminary data from gut samples collected by [name] in other recent projects. Given this variance, and with a balanced design of $n=50$ in the experimental and control arms ($N=100$ total), we will have >99% power to detect a 1 unit increase in Shannon Index. Power for Aim 2 is based on changes in serum SCFAs. Our SCFA assays will be performed at Metabolon and our colleagues at Metabolon provided information on mean \pm SD for these outcomes in their lab. They are as follows: acetate= 1806 ± 2500 ng/mL, butyrate= 35 ± 43 ng/mL, and propionate= 50 ± 52 ng/mL. With these distributions, we will have >80% power to detect a difference in SCFA levels between treatment and control groups with a magnitude of at least 50% of 1 SD.

The primary outcome for Aim 3 will be a composite score based on the average of the z-scores for the following 5 biomarkers: HDL-C, fasting glucose, triglycerides, average of systolic and diastolic BP, and waist circumference. The standardized mean \pm SD of this *CMDrisk* z-score in [name] sedentary behavior intervention among 575 participants (Grant #: R01CA198971) is 0 ± 0.7 . This provides 80% power to detect a difference in the *CMDrisk* z-score of 0.4, between intervention and control at the conclusion of the study.

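### Recruiting 150 does not give the 100 completers of section 10.1 if both stated loss rates apply to every recruit, and the 80% power in 15.2 for Aim 3 has no margin for the shortfall

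*Combined protocol and SAP*

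**What the plan says.** Section 10.1 sets out two losses. On the first: "We will assume a 20% attrition rate based on documented attrition rates of PA interventions". The second is a "30% rate of individuals who fail to fall within the HbA1c eligibility range during screening". It presents the recruitment number as chosen in light of both: "we will recruit 150 individuals total to meet our desired overall N of 100 participants (n = 50 per group").

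Section 15.2 gives the sample size once, in the Aim 1 sentence, as a balanced n=50 "in the experimental and control arms". For Aim 2 it says "we will have >80% power to detect a difference in SCFA levels between treatment and control groups" of at least half an SD. For Aim 3, with a CMDrisk SD of 0.7, it says "This provides 80% power to detect a difference in the" CMDrisk score of 0.4. No n is repeated for Aims 2 and 3, so 50 per arm is the natural reading but is not stated. Section 15.2 mentions neither attrition, alpha nor sidedness.

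Elsewhere 100 is simply the size of the trial. Section 1.1: "We propose a 100-participant randomized controlled 2-arm parallel trial". Section 5.1: "We will employ a 100-participant, 8-wk, randomized 2-arm parallel trial design with a 1:1 allocation ratio".

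**The concern.** Section 10.1 links 150 to 100 through two rates, but applying them in sequence does not lead from one to the other. Section 15.2 then takes 50 per arm as the number analysed.

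The blood outcomes are the most exposed. Section 5.2 omits the fasting draw at week 4, so a participant lost before week 8 has no post-baseline SCFA, lipid or glucose value. That removes all of Aim 2 and most components of CMDrisk. Section 12.2 says data already collected will be used under intent-to-treat, but it collects nothing further after voluntary withdrawal, and no imputation method is given.

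If fewer than 50 per arm complete, a null result for Aim 2 or Aim 3 would be read against a power that the plan's own assumptions do not deliver.

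**Working it through.** **Inputs.** From 10.1: 150 recruited, 30% HbA1c failure, 20% attrition, target 100 (50 per arm). From 15.2: Aim 1, 1 unit on SD 0.6 (d = 1.667); Aim 2, d = 0.5; Aim 3, 0.4 on SD 0.7 (d = 0.571). Alpha is assumed to be 0.05, and both one-sided and two-sided tests are shown because the plan states neither.

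**Method.** Two-sample t-test, n per arm, power from the noncentral t with 2n - 2 degrees of freedom and noncentrality d x sqrt(n/2).

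**The plan's own figures at 50 per arm.**
- Aim 3: 80.8% two-sided, which matches the stated 80%; 88.4% one-sided, which does not.
- Aim 2: 69.7% two-sided; 79.9% one-sided, which is close to the stated threshold.
- Aim 1: above 99% either way, as stated.

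**Completers if 100 means completing.** Let s be the share of recruits exposed to the 30% failure. Completers = 150 x (1 - 0.30s) x 0.80.
- s = 1: 150 x 0.70 x 0.80 = 84 (42 per arm)
- s = 0.75: 150 x 0.775 x 0.80 = 93
- s = 0.5: 150 x 0.85 x 0.80 = 102
- Break-even for 100: s = (1 - 100/120)/0.30 = 0.556

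**Completers if 100 means randomised.** 150 x 0.70 = 105, so 150 is enough to randomise 100.
- All of the 20% lost after randomisation: 100 x 0.80 = 80 (40 per arm).
- Half of it lost in the 3-week run-in, before randomisation: 0.90 x (1 - b) = 0.80, so b = 0.111 and about 89 complete (44 per arm). The documents do not give the split.

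**Power at those numbers.**

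| n per arm | Aim 3, two-sided | Aim 3, one-sided | Aim 2, one-sided |
|---|---|---|---|
| 50 | 80.8% | 88.4% | 79.9% |
| 49 | 79.96% | 87.8% | 79.2% |
| 46.5 (93 complete) | 77.8% | 86.2% | 77.3% |
| 44 | 75.5% | 84.5% | 75.2% |
| 42 | 73.5% | 83.0% | 73.5% |
| 40 | 71.4% | 81.3% | 71.6% |

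Two-sided, Aim 2 goes from 69.7% at 50 to 62.0% at 42 and 59.8% at 40. Its gap at 50 per arm is a separate matter and is not counted here. Aim 1 stays above 99% at 40.

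**Detectable difference at 80% two-sided power.** At 50 per arm: 0.566 SD, or 0.566 x 0.7 = 0.40 on CMDrisk. At 42: 0.619 SD, or 0.43. At 40: 0.634 SD, or 0.44.

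**The case against.** The strongest reply is that the plan did allow for attrition. Section 10.1 names both rates and presents 150 as the number that meets 50 per group in spite of them, and 15.2 then uses that n. This stands. A reader might infer from the silence in 15.2 that attrition was overlooked; the wording of 10.1 does not support that. The fault is that the allowance in 10.1 does not add up if both rates apply to everyone.

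A second reply is that the 30% need not apply to everyone. Section 8.1 admits people on documented prediabetes, 8.3 tests HbA1c in those who still need confirmation, and 22.1 expects recruitment mainly from partner clinics. This also stands: at about 56% tested or fewer, 150 yields 100 completers and there is no shortfall. But the plan does not give the share, so the reader cannot tell.

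A third is that 40 per arm rests on reading 100 as the number randomised. Sections 1.1 and 5.1 fit that reading, but 10.1 uses attrition to get from 150 to 100, which makes sense only if 100 is net of it. So 40 per arm is the weaker case.

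Loss of data may also fall below 20%, because 12.1 still invites people who stop exercising through illness or injury to all measurements.

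Finally, adjusting for baseline CMDrisk could recover the power: at 42 per arm a baseline to week 8 correlation of sqrt(1 - (0.5714/0.6186)^2) = 0.38 would restore 80%. The Aim 3 covariates in 15.3 do not include baseline CMDrisk, so the plan cannot claim this gain as written.

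**Conclusion.** The point holds in a limited form. If both rates in 10.1 apply to all recruits, 150 gives 84 completers, not 100. At two-sided 0.05, the stated Aim 3 power needs every one of the 50 per arm, so any shortfall takes it below 80%, to 73.5% at 42 per arm. At one-sided 0.05 Aim 3 is safe, while Aim 2, a primary outcome, goes from 79.9% to 73.5% at 42. Because Aim 2 is already marginally short of its claim before any loss, attrition widens that miss; it does not create it. Aim 1 is not affected.

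A reader might conclude that Aim 3 simply has 71 to 74% power, or that enrolment must rise to 100/(0.70 x 0.80) = 179. The documents support neither. Those powers are the low end of a range that runs up to 80.8%, depending on the tested share, the meaning of 100 and the timing of losses, none of which the plan states. The figure of 179 assumes that every recruit faces the 30%.

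The calculation assumes alpha 0.05, an unadjusted two-group comparison, 50 per arm for all aims, and the SD of 0.7 as given. Section 15.2 ties that SD to a five-component score with waist circumference, while 5.2 lists the score without waist; that discrepancy is separate and is not included here.

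**What to change.** In 10.1, correct the step from 150 to 100: say whether 100 is the number randomised or the number completing, say to whom the 30% HbA1c failure applies and in what expected share, and give the number of completers that follows.

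In 15.2, state alpha, sidedness and the n used for each aim, and restate power and detectable differences for Aims 2 and 3 at that expected number of completers. The number should follow from the clarified 10.1 and not be fixed in advance. If both rates do apply to all recruits, it is 42 per arm, with a detectable difference of 0.62 SD (0.43 on CMDrisk) at 80% two-sided power.

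The cost is wording in two sections and possibly less favourable stated figures. No added enrolment, visits or assays are required.

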11.0 Local Recruitment Methods

11.1 Recruitment Process: Participants will be recruited on a rolling basis through a combination of the following methods: clinical referrals via partners within community-based health clinics, mass emails via University of Minnesota-Twin Cities campus listservs (all permissions will be obtained prior to this method), emails to past study participants who gave permission for future contact, and fliers posted on physical (e.g. campus buildings, community billboards) and virtual (e.g. Facebook, NextDoor) walls. Our study will also be searchable through clinicaltrials.gov and studyfinder.umn.edu.

Should additional recruitment methods be needed, we may also use established recruitment databases and EMR obtained through partial HIPAA waiver (which we have had approved). For instance, we may use the patient access database overseen by the Clinical and Translational Science Institute.

This study will also be listed at ResearchMatch.org. ResearchMatch is an electronic volunteer recruitment registry that allows people from anywhere in the country to self-register and express an interest in being prospectively considered for participation in research studies. This registry provides information about those volunteers to researchers who are looking for people to participate in studies, while protecting the privacy of the volunteers.

We intend to begin this recruitment process in early 2021, and we believe we can recruit the requisite number of participants over one year.

11.2 Identification of Potential Participants: Participants will be referred by one of our partnering care providers or will self-identify in response to fliers, emails, or internet postings.

- Potential participants will make the initial contact with study staff by telephone, mail, text, or via completion of our online screening survey. Only after this initial contact will study staff reach back out to potential participants.

11.3 Recruitment Materials: All study materials (fliers, postcards, emails) will contain a brief description of the study, primary inclusion criteria, a link to our study screening survey, and our contact information. Clinical

MEDICAL PROTOCOL (HRP-590)

PROTOCOL TITLE: Exercise and the Gut Microbiome R21

VERSION DATE: 05/11/2022

recruitment partners will receive materials in their preferred method, such as a small study postcard for placement in their lobby, or the same flier that we intend to post within community-based spaces such as local community centers. Emails sent will include the community flier as an attachment, while also containing similar text within the body of the email, along with a direct link to our study screening survey.

11.4 Payment: Participants will have the choice of one of two incentives for study completion with greater than 80% adherence: (1) they may request \$100 following their completion of the entire study, with this payment provided using the Greenphire ClinCard; OR (2) they may request to keep the Fitbit Inspire 2 along with a \$25 ClinCard. This amount is reasonable given the study's protocol and procedures.

12.0 Withdrawal of Participants

12.1 Withdrawal Circumstances: We do not foresee any circumstances under which participants will be withdrawn from the research without their consent. Participants who discontinue from the active intervention due to illness or injury will still be invited to complete all study measures at all data collection time points.

12.2 Withdrawal Procedures: For participants who ask to withdraw from the study voluntarily, no additional data will be collected and participants would be compensated at the prorated rate as described in Section 11.4. would still be compensated according to the table above. However, data from the participant's time in the study will still be used in data analysis when employing an intent-to-treat analysis approach.

12.3 Termination Procedures: We do not foresee any circumstances that would result in the termination of the study for any individual.

13.0 Risks to Participants

13.1 Foreseeable Risks: The current study present no greater than minimal risk to participants. However, we will be taking precautions to ensure any potential risk from study participation is minimized. Per standard procedures during exercise intervention studies, we will ensure participants have no contraindications to exercise participation. However, we must note that any type of physical activity participation, even a walking exercise intervention like that of the current study, does carry risk in any population. Risks associated with exercise participation include

MEDICAL PROTOCOL (HRP-590)

PROTOCOL TITLE: Exercise and the Gut Microbiome R21

VERSION DATE: 05/11/2022

dizziness, nausea, muscle soreness, fatigue, fainting, joint pain, shortness of breath, muscular strains/sprains, and cramping. We will minimize these risks by allowing participants to complete a 5-10-minute warm-up of slow walking prior to each exercise session.

Some potential psychological stress or embarrassment may also be associated with filling out the study questionnaire and/or undergoing measurements of weight, waist circumference, and blood pressure in addition to the collection of stool samples and saliva. Risks will be minimized by collecting this data in a private setting, either at their home or at the ECRC, depending upon the measure in question.

As with all blood draws, there may be a modest amount of pain (equivalent to that of a pin prick) and lightheadedness associated with the collection of approximately 3 tablespoons of blood for each of three blood draws. We will minimize this risk by employing an experienced and trained phlebotomist for blood draws. Overall, the anticipated benefits to science outweigh the risks.

Finally, to prevent any threat of a COVID-19 infection, we will follow all UMN/OVPR/ECRC protocols while the participant is at the ECRC and encourage masking and physical distancing if any walks are done outside of the ECRC environment.

13.2 Reproduction Risks: N/A

13.3 Risks to Others: N/A

14.0 Potential Benefits to Participants

14.1 Potential Benefits: Throughout the course of the 8-week intervention, participants may improve cardiometabolic indices (e.g., blood lipids, fasting insulin/glucose, blood pressure, c-reactive protein) while possibly experiencing weight loss too.

15.0 Statistical Considerations

15.1 Data Analysis Plan: Chi-square and independent *t*-tests will evaluate baseline group differences as appropriate. Mediation analyses will also be conducted. We outline our analysis plans in Section 15.3. ⁸⁶⁻⁹²

MEDICAL PROTOCOL (HRP-590)

PROTOCOL TITLE: Exercise and the Gut Microbiome R21

VERSION DATE: 05/11/2022

15.2 Power Analysis: Power for Aim 1 is based on analyses using alpha-diversity (Shannon Index) as the primary outcome. Taniguchi et al.⁴⁶, reported a mean \pm SD baseline Shannon Index of 5.7 ± 0.6 which is consistent with preliminary data from gut samples collected by [name] in other recent projects. Given this variance, and with a balanced design of $n=50$ in the experimental and control arms ($N=100$ total), we will have >99% power to detect a 1 unit increase in Shannon Index. Power for Aim 2 is based on changes in serum SCFAs. Our SCFA assays will be performed at Metabolon and our colleagues at Metabolon provided information on mean \pm SD for these outcomes in their lab. They are as follows: acetate= 1806 ± 2500 ng/mL, butyrate= 35 ± 43 ng/mL, and propionate= 50 ± 52 ng/mL. With these distributions, we will have >80% power to detect a difference in SCFA levels between treatment and control groups with a magnitude of at least 50% of 1 SD.

The primary outcome for Aim 3 will be a composite score based on the average of the z-scores for the following 5 biomarkers: HDL-C, fasting glucose, triglycerides, average of systolic and diastolic BP, and waist circumference. The standardized mean \pm SD of this *CMDrisk* z-score in [name] sedentary behavior intervention among 575 participants (Grant #: R01CA198971) is 0 ± 0.7 . This provides 80% power to detect a difference in the *CMDrisk* z-score of 0.4, between intervention and control at the conclusion of the study.

15.3 Statistical Analysis: Aim 1 analysis: Gut microbiome data, derived via metagenomic sequencing, will be operationalized as described above. In a primary analysis, generalized linear regression models will regress Shannon Index on intervention assignment. The model is formalized as: $E[Y] = \text{intercept} + \beta_1 * A + \beta_2 * C$. $E[Y]$ =expected Shannon value; β_1 =coefficient for intervention arm; β_2 =coefficient for a vector of confounders should this be necessary in our randomized design. Secondary analyses will consider metagenomic features (genes and functional profiles). Any metagenomic features not present at >0.1% relative abundance in at least 10% of samples will be removed. Zero-inflated log-linear generalized linear models with a Gaussian error term will be fitted, with treatment status as predictor, as implemented by the metagenomeSeq Bioconductor package for shotgun metagenomic data analyses.⁹³ The generalized model, per metagenomic outcome, is formalized as: $\log E[Y] = \text{intercept} + \beta_1 * A + \beta_2 * C$. $E[Y]$ =expected normalized sequence count value; β_1 =coefficient for intervention arm; β_2 =coefficient corresponding to the vector of baseline confounders. Total read count is incorporated as an offset term. This analysis will generate a “top list” of genes, gene families, and pathways with altered abundance by intervention assignment. Separate models will

MEDICAL PROTOCOL (HRP-590)

PROTOCOL TITLE: Exercise and the Gut Microbiome R21

VERSION DATE: 05/11/2022

be developed for intervention status predicting week 4 and week 8 outcomes. We will also consider time*treatment status models to incorporate stool sampling at all three timepoints. P-values will be corrected for multiple hypothesis testing using the false-discovery rate as we have done previously with high dimensional data.^{86-92,94-98}

Aim 2 analysis: As with Aim 1, generalized linear regression models will be used. Each of three SCFAs (acetate, butyrate and propionate) will be regressed on intervention assignment. The model is formalized as: $E[Y] = \text{intercept} + \beta_1 * A + \beta_2 * C$. $E[Y]$ =expected SCFA value; β_1 =coefficient for intervention arm; β_2 =coefficient for a vector of confounders.

Aim 3 analysis: We will use PROC CAUSALMED (SAS 9.4) to explore **mediation** effects on *CMDrisk*. This regression-based model was developed by Valeri and VanderWeele⁹⁹ and VanderWeele.¹⁰⁰ The predictor variable will be treatment (experimental vs. control) and the outcome will be *CMDrisk*. We will include age, *sex as a biological variable*, race/ethnicity, and PA duration as covariates. Mediation will be tested by adding parameters, *in separate models*, for gut microbiota diversity (8-week change in β -diversity) and serum SCFAs (8-week change in levels of serum SCFAs).

15.4 Data Integrity: All data will be double entered separately by two individuals. Blood and stool sample data will be examined for computational value errors associated with out-of-range variables. All data will be examined for outliers and improbable values. More details provided in section 17.1.

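### Aim 2 power: more than 80% for a 0.5 SD difference in serum SCFAs does not follow from 50 per arm at two-sided 5% unadjusted (about 70%)

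*Combined protocol and SAP*

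**What the plan says.** Section 15.2 sets 50 participants per arm. For Aim 2 it opens with "Power for Aim 2 is based on changes in serum SCFAs", then lists means and SDs supplied by the assay laboratory: acetate 1806 (SD 2500), butyrate 35 (43) and propionate 50 (52) ng/mL. From these it claims ">80% power to detect a difference in SCFA levels between treatment and control groups with a magnitude of at least 50% of 1 SD".

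For Aim 3 the same section gives the composite risk score an SD of 0.7. It continues with "This provides 80% power to detect a difference in the" composite score of 0.4, "between intervention and control at the conclusion of the study".

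In Section 15.3 the Aim 2 model is stated as "Each of three SCFAs (acetate, butyrate and propionate) will be regressed on intervention assignment", with a further term for confounders that are not listed. Baseline SCFA is neither named nor excluded. Section 1.1 words the hypothesis directionally: "Serum Levels of SCFAs butyrate, acetate, and propionate will increase after 8 weeks in the experimental group vs. control". No alpha and no sidedness are given for any aim. The only error-rate statement, "P-values will be corrected for multiple hypothesis testing using the false-discovery rate", stands under the Aim 1 analysis.

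**The concern.** When the effect is expressed in SD units, the listed SCFA SDs cancel. Power then depends only on the number per arm, alpha, sidedness and any baseline adjustment. Fifty per arm is a familiar size, and 0.5 SD at two-sided 5% normally needs more than that for 80% power. The Aim 3 sentence sharpens the question: it claims 80% power at a larger standardised difference (0.4/0.7 = 0.57) with the same 50 per arm, while Aim 2 claims more than 80% at 0.50.

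The sentence is the only justification of N=100 for a primary outcome. If the power is overstated, a null Aim 2 result will be read as stronger evidence against a 0.5 SD effect than it is.

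**Working it through.** **Inputs.** From Section 15.2: n = 50 per arm; Aim 2 difference d = 0.5; Aim 3 difference 0.4 with SD 0.7. Alpha of 5% is an assumption, shown two-sided and one-sided. All baseline correlations r are assumptions, because the documents give none. Fifty analysed per arm is taken as stated.

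**Method.** Two-sample comparison by noncentral t with 98 df and noncentrality d × √(n/2) = d × √25 = 5d. The normal approximation is shown as a check.

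**Step 1: find a convention that reproduces a figure in the section.** For Aim 3, d = 0.4/0.7 = 0.571 and the noncentrality is 2.857. Two-sided 5%: 80.8% (normal approximation Φ(2.857 − 1.960) = 81.5%). This matches the stated 80%. One-sided 5% gives 88.3%. The Aim 1 figure does not help to choose: at d = 1/0.6 power exceeds 99% even two-sided.

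**Step 2: apply the same convention to Aim 2.** The noncentrality is 5 × 0.5 = 2.5.

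- Two-sided 5%: 69.7% (normal approximation Φ(2.5 − 1.960) = 70.5%).
- One-sided 5%: 79.9% (normal approximation Φ(2.5 − 1.645) = 80.4%).

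**Step 3: what 80% would need at two-sided 5%, unadjusted.** At 0.5 SD, 64 per arm (63 by normal approximation). With 50 per arm, the detectable difference is 0.566 SD:

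| SCFA (ng/mL) | 0.5 SD | 0.566 SD |
|---|---|---|
| Acetate | 0.5 × 2500 = 1250 | about 1415 |
| Butyrate | 0.5 × 43 = 21.5 | 24.3 |
| Propionate | 0.5 × 52 = 26.0 | 29.4 |

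**Step 4: use of the baseline value, two-sided 5%.** With baseline as covariate, d becomes 0.5/√(1 − r²), 97 df. As a change score, d becomes 0.5/√(2(1 − r)), 98 df.

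| Assumed r | Baseline as covariate | Change score |
|---|---|---|
| 0.30 | 73.7% | 55.3% |
| 0.47 | 80.1% | 67.2% |
| 0.50 | 81.5% | 69.7% |
| r needed for 80% | about 0.47 | about 0.61 |

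If the 0.5 SD were instead meant in units of the SD of change, d is again 0.5 and power is again 69.7%.

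**Multiplicity.** All figures above are per SCFA and before any correction. The text does not say whether the three SCFAs are corrected. For scale only, at an assumed 0.05/3, two-sided and unadjusted, power is 52.8%.

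**The case against.** The strongest reply is that two-sided 5% without adjustment is the reader's assumption, not the plan's. The plan declares no test, and two readings bring the figure to about 80% or above.

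- **One-sided test.** The Aim 2 hypothesis is directional, and the normal approximation gives 80.4%. But no one-sided test is declared, the t calculation gives 79.9%, and Aim 3 would then be 88.3% rather than 80%. One could argue that 0.4 is a rounded 0.35, half of 0.7, in which case a single one-sided test would fit both sentences. That requires replacing a stated input with a different one.
- **Rounding of the Aim 3 SD.** With a difference of 0.4, an SD anywhere from 0.65 to 0.75 gives 86.1% to 75.2% two-sided. So the 80.8% match is supporting evidence, not proof, of a two-sided convention. This stands.
- **Baseline adjustment.** The Aim 2 power is said to rest on changes, whereas Aim 3 is a comparison at study end. Fasting blood is drawn at baseline and week 8, and the Aim 3 mediation uses "8-week change in levels of serum SCFAs". If only Aim 2 is baseline-adjusted with r of about 0.47 or more, both power sentences hold at two-sided 5%. This too stands as a possibility. But the SDs supplied are not described as SDs of change, no correlation is given, and baseline SCFA is not named in the Aim 2 model. A literal change-score analysis needs r of about 0.61.

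The stated figure is therefore not impossible. Each route to it needs an assumption that the documents do not contain.

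**Conclusion.** The point holds. With 50 analysed per arm, two-sided 5%, no baseline adjustment and no multiplicity correction, power for a 0.5 SD difference in each SCFA is 69.7%, about 10 percentage points below the claim. The chance of missing such an effect is about 30%, and 80% power is reached at 0.566 SD. Taking the inputs as stated, the Aim 2 and Aim 3 power sentences cannot both be right under one common unadjusted test. They can both be right if Aim 2 alone is baseline-adjusted with sufficient correlation, but the plan does not say so, and a reader cannot check the figure. This should be corrected. It does not call the design or the planned analyses into question.

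**What to change.** In Section 15.2, state one alpha and one sidedness for all aims, and the variance basis for Aim 2. Then choose one of the following.

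1. **Restate the power.** Replace the Aim 2 sentence with: *With 50 analysed per arm, two-sided alpha 0.05, no baseline adjustment and before any multiplicity correction, the trial has about 70% power per SCFA for a 0.5 SD difference; 80% power is reached at about 0.57 SD.*
2. **Adjust for baseline.** Name baseline SCFA as a covariate in the Aim 2 model in Section 15.3. In Section 15.2 give the assumed correlation, its source and the resulting power. About 0.47 or more is needed for 80%; 0.5 gives 81.5%, before any multiplicity correction.
3. **Declare a one-sided 5% test**, if that is intended, and restate Aim 2 as about 80% and Aim 3 as 88.3%.

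The cost is one or two sentences in Section 15.2, plus one named covariate in Section 15.3 for the second option. The first option makes the stated power less favourable. None of them needs extra participants or procedures.
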